3.2.2 Exclusion criteria

1. patient undergoing cardiac surgery, cranial surgery
2. known history of dementia
3. unavailability of tablet or computer with an internet connection for remote assessment
4. patient unable to interact with a tablet or computer due to language, visual, or hearing impairment, or any severely limited mobility of the upper limb joints
5. patient unable to understand spoken or written English
6. surgery delayed for an intercurrent clinical event

3.3 Recruitment and procedures

Eligible patients will be first approached by members of their circle of care. We have engaged surgeons from different disciplines at the participating sites. and we will distribute (via email) study information, including eligibility criteria, across surgical practices. The study team will be in periodic contact with surgical practices to look for potential participants. Members of the patient circle of care will ask the potential participants for permission to share their contact with the research team. The study will be then all conducted remotely, by videoconference (baseline) or telephone (follow-ups), with McMaster University as the coordinating and assessment centre. The study team will be in periodic contact with the participating surgical practices to look for potential participants. An informed verbal consent will be sought. After the first contact of the research team with the patient, an informative written document including the same information conveyed during the verbal consent process will be sent to the participant using the same email address that will be used during the study to deliver the link to the computerized tests. At the next call, once the patient has had a chance to review the document, the research personnel will look for confirmation of their consent to participate, before proceeding to any assessment.

If the patient agrees to participate, the patient will be allowed, if necessary, to involve in the study a next of kin or support who can help facilitate the access to an electronic device with an internet connection which will be used to administer the cognitive battery remotely, and the training on the battery.

The research team will set up an initial videoconference with the participant (and the next of kin/support if necessary) to explain the Cogstate Brief Battery (CBB), i.e. the internet-based cognitive testing, and train on self-administration. Zero to 3 days before each scheduled cognitive assessment the participant (or the next of kin/support) will be emailed a user-specific

link to the cognitive program. Around the same time the participant will receive a telephone call to remind to complete the assessment.

The baseline videoconference-based visit with the patient will be conducted using different software options, as long as they allow screen sharing, including Skype and Zoom, based on availability and participant discretion. The subsequent calls will be done using the telephone.

We will seek confirmation of consent to participate in the study during the initial videoconference, and at every telephone contact with the patient throughout the study.

3.4 Measurements

At the initial videoconference, data on baseline characteristics will be collected, including demographics, social history, comorbidities, and relevant pharmacological and non-pharmacological (e.g. radiation) therapies. At the initial videoconference the questionnaire to explore change in activities and participation since COVID-19 will be also administered.

At each of the calls that will remind the self-administered cognitive assessment, the research team member will also

- 1) ask about any clinically relevant intercurrent event (i.e. hospital admissions, ED visits, visits to urgent care, changes in medications);
- 2) assess mobility/physical function based on the Late Life Function and Disability Instrument: Function Component (LLFDI), and life space mobility questions
- 3) assess depressive symptoms using the Geriatric Depression Scale (GDS)
- 4) assess pain using a Numeric Pain Rating Scale (NPRS)

Data on the participant past medical history, medication, date and type of surgery, postoperative course, and intercurrent clinical events will be obtained from the interview with participant, and confirmed or completed through review of electronic hospital medical records, based on the execution of a Data Transfer Agreement between McMaster University and Hamilton Health Sciences Corporation. If needed, for data completion or clarification, the participant's family physician will be also contacted.

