Follow-up and measurements	At enrolment and monthly before surgery (i.e. ≥ 2 preoperative assessments per patient), and then 1 month, 3 months, 6 months, and 12 months after surgery, patients will be assessed remotely 
 1. on their cognitive performance, through a computerized brief cognitive test battery, self-administered, i.e. the Cogstate Brief Battery (CBB) 2. on their physical function/mobility, through the Function Component of the Late-Life Function and Disability Instrument (LLFDI-FC) and exploring life space mobility

	
3. on their depressive symptoms, through the short form (15-item) version of the Geriatric Depressive Scale (GDS)4. on their pain, through a Numeric Pain Rating Scale (NPRS)
--	--

Table of Contents

1. BACKGROUND AND RATIONALE.....	5
2. OBJECTIVES.....	6
3. METHODS	6
3.1 Study design.....	6
3.2 Study population.....	6
3.2.1 Inclusion criteria.....	7
3.2.2 Exclusion criteria.....	7
3.3 Recruitment and procedures	7
3.4 Measurements	8
3.4.1 Cogstate Brief Battery (CBB).....	8
3.4.2 Changes in activities and participation since COVID-19 questionnaire.....	9
3.4.3 Late Life Function and Disability Instrument: Function Component (LLFDI-FC).....	9
3.4.4 Geriatric Depression Scale (GDS).....	10
3.4.5 Numeric Pain Rating Scale (NPRS)	10
3.5 Sample size.....	10
3.6 Data analysis plan.....	11
3.6.1 Primary analysis.....	11
3.6.2 Secondary Analyses	12
4. IMPORTANCE OF THE STUDY	12
APPENDIX I. Study timeline, measurements, and data collection	14
APPENDIX II. Performance at the Cogstate One-Back Task (OBK): interpretation and clinical relevance of changes in score.....	15
APPENDIX III. Changes in activities and participation since COVID-19 questionnaire	16
REFERENCES.....	17

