3.4.3 Late Life Function and Disability Instrument: Function Component (LLFDI-FC)

The Function Component of the Late-Life Function and Disability Instrument (LLFDI-FC) is a widely used patient-reported outcome of physical function.^{14 15} It comprehensively assesses discrete functional tasks and operationalizes disability in important life roles beyond the narrow construct of activities of daily living. Extensive evidence supports its construct validity and sensitivity to change among various clinical populations of community-dwelling older adults.¹⁶ The instrument will be administered over the phone by the research personnel at each follow-up, preoperatively and postoperatively. Three additional questions will be also asked to explore life space mobility (being just outside the house, being in the neighborhood, and being outside

the neighborhood), which will also capture changes in social distancing policy that we expect will happen over the study period. At the end of the mobility questionnaire, the participants will be also asked whether there have been changes in their ability of performing basic and instrumental activities of daily living.

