3.6.2 Secondary Analyses

We will explore whether the effect of surgery on cognitive trajectories differ based on baseline patient characteristics, including age, type of surgery, cognitive performance at baseline, comorbidities, mobility, GDS and pain score. This will be done studying the interaction of these covariates with the components of the interrupted time analysis. The interrupted time series approach as described assumes linearity and constancy of the preoperative trend when projected postoperatively. We will evaluate the validity of these assumptions exploring the association of changes in cognitive performance with intercurrent events other than the index surgery, for the long-term effects.

With a similar approach as for the cognitive performance, we will study the perioperative trajectories of patient physical function/mobility (as indicated by the LLFDI-FC and the life space mobility questions), depressive symptoms (as indicated by the GDS), and of pain (as indicated by the NPRS). We will also explore whether the time-dependent LLFDI-FC, GDS and NPRS scores are associated with the time-dependent cognitive scores.

STATA software, version 15, will be used for the analyses.

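### The life-space answers, which the plan expects to move with distancing policy, are modelled around surgery as patient mobility with no calendar or policy term

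*Combined protocol and SAP*

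**What the plan says.** Section 3.4.3 adds three questions to the LLFDI-FC, on being just outside the house, in the neighbourhood and beyond it. It gives the answers a second role: "which will also capture changes in social distancing policy that we expect will happen over the study period".

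Elsewhere the same answers stand for the patient's own function:
- Study summary, follow-up and measurements: patients are assessed "on their physical function/mobility, through the Function Component of the Late-Life Function and Disability Instrument (LLFDI-FC) and exploring life space mobility".
- 3.4 Measurements: at each reminder call the team will "assess mobility/physical function based on the Late Life Function and Disability Instrument: Function Component (LLFDI), and life space mobility questions". Appendix I puts both instruments in one row.
- 3.6.2 Secondary Analyses: "With a similar approach as for the cognitive performance, we will study the perioperative trajectories of patient physical function/mobility". Two indicators of this outcome are then named: the LLFDI-FC and the life-space answers.

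The cognitive approach in 3.6.1 is an interrupted time series with a preoperative slope, a level change around surgery and a change in slope. Section 3.6.2 says that this approach "assumes linearity and constancy of the preoperative trend when projected postoperatively". It will examine the assumption by "exploring the association of changes in cognitive performance with intercurrent events other than the index surgery". Section 3.4 defines intercurrent events as hospital admissions, emergency or urgent care visits, and medication changes.

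**The concern.** The plan expects an influence from outside the patient to move this measure during follow-up, yet models the change in the measure around surgery as a change in the patient. Nothing in 3.6 separates the two. No calendar-time, site-policy or restriction term is named, the assumption check covers only cognition and clinical events, and no analysis uses the life-space answers as a policy covariate.

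The timing makes this a practical risk. Enrolment is planned for May to August 2020, surgery falls at least 6 weeks later, and follow-up runs to 12 months after surgery. Preoperative and postoperative calls therefore fall in different calendar periods. Section 1 relies on the actual preoperative trajectory to absorb the effect of restrictions. That cannot cover a restriction that changes after surgery, or one that changes abruptly before it.

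At stake is the mobility part of the secondary objective in section 2. A change in the rules on leaving home could be reported as a change in physical function after surgery.

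**Working it through.** **1. The plan's own figure.** The only sample size is for the One-Back hypothesis (3.5): SD 0.16, decreases of 0.009 and 0.035, two-sided alpha 0.05, power 80%, attrition 10%.

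n = [0.16 × 2.8016 / (0.035 − 0.009)]² = 297.2, and 297.2 / 0.90 = 330.3. This reproduces 330. Nothing below changes it, and the documents give no SD, effect size or power for life space.

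**2. How a policy change enters the model.** Let surgery have no effect, and let a reopening raise the life-space score. The effect 6 months after surgery, relative to the projected preoperative trend, is

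contrast = level change + 6 × (change in slope per month).

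If the score rises before surgery, the preoperative slope is steep. The model projects that rise forward, and a score that merely stays at its reopened level looks like a loss. If the score rises after surgery, the preoperative slope is flat and the rise looks like recovery.

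**3. Illustration.** All of these inputs are assumptions, except that 297 is 330 less 10%:
- 297 patients enrolled evenly over 120 days, with surgery 42–90 or 42–180 days later.
- Calls every 30 days before surgery, then 1, 3 and 6 months after.
- Within-patient residual SD of 1 (the unit below) and no surgery effect.
- One reopening worth 1 SD, starting 60, 120, 180 or 240 days after enrolment opens, either as a step or spread over 90 days.
- Within-patient fit with common slopes, averaged over 25 simulated studies per scenario.

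Contrast at 6 months, in SD, with no policy term:

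| Reopening starts | Wait 42–90 d, step | Wait 42–90 d, gradual | Wait 42–180 d, step | Wait 42–180 d, gradual |
|---|---|---|---|---|
| Day 60 | -1.39 | -0.86 | -0.60 | -0.91 |
| Day 120 | -0.78 | +0.21 | -0.95 | -0.31 |
| Day 180 | +0.97 | +0.82 | -0.02 | +0.50 |
| Day 240 | +0.95 | +0.66 | +0.76 | +0.64 |

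Eight values are positive, one is about zero and seven are negative. The two extremes, from rounded coefficients:
- Day 60, short wait, step: preoperative slope +0.23 per month, level change -0.02, slope change -0.23. Contrast = -0.02 + 6 × (-0.23) = -1.40 (-1.39 unrounded).
- Day 180, short wait, step: preoperative slope +0.01, level change +0.24, slope change +0.12. Contrast = 0.24 + 6 × 0.12 = +0.96 (+0.97 unrounded).

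The unmodelled mean, all postoperative calls minus all preoperative calls, rises in every scenario, by 0.18 to 0.73 SD.

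**4. Other sizes.** The bias is proportional to the assumed shift. For 0.5 SD the range is 0.5 × (-1.39) = -0.70 to 0.5 × 0.97 = +0.49. For 0.2 SD it is 0.2 × (-1.39) = -0.28 to 0.2 × 0.97 = +0.19.

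**5. With the policy term.** When the true policy indicator is in the model, the 6-month contrast lies between -0.16 and +0.10 SD. The fitted model then matches the generating one, so the remainder is simulation noise. Adjustment works because surgery dates are staggered over months.

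**The case against.** The strongest reply is that life space properly reflects environment as well as ability. Section 2 aims only to describe mobility trajectories and explore their link with cognition, and the sentence in 3.6.1 attributing the level change to surgery speaks of cognitive performance. Nor do the documents say that the life-space answers and the LLFDI-FC are combined, so separate reporting would show any divergence. The absence of a stated composite is a fair limit on the point. The rest does not remove it: 3.6.2 carries the cognitive approach over to mobility, and a measure partly driven by policy cannot have its change around surgery interpreted without accounting for policy.

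Four stronger readings are tempting but unsupported.
- *A reopening will be read as recovery.* The sign depends on timing, as the table shows.
- *A false surgery effect is almost certain.* A raw pre-post change with SD 1 in 297 patients has standard error 1/√297 = 0.058. A bias of 0.25 to 0.50 SD would then give z of 4.3 to 8.6, and a bias of 0.10 SD would give about 41% false positives. Those figures belong to a raw difference, not the planned model. In a simple segmented model with 2–3 preoperative visits, the standard error of the 6-month contrast is about 0.21 to 0.39 SD, and a bias of 0.10 SD would be declared significant about 6–8% of the time. The shifts themselves are invented.
- *Subgroup results by baseline mobility would be enrolment-date effects.* Section 3.6.2 lists mobility as a modifier without saying that it includes life space. It needs a definition; no more can be concluded.
- *Life space contaminates the time-dependent function score.* Section 3.6.2 already names the LLFDI-FC alone there.

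One further objection stands: section 1 expects restrictions to affect physical performance, mood and pain too, so relying on the LLFDI-FC alone does not remove calendar-time confounding.

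**Conclusion.** The point holds as a weakness in one indicator of a secondary objective. The plan expects distancing policy to move the life-space answers, treats them as patient physical function, and models them around surgery without a term for calendar time or policy. A policy change can then bias the estimated surgery effect on mobility in either direction.

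The size cannot be derived from the documents. The range of -1.39 to +0.97 SD rests on an assumed 1 SD reopening, an assumed reopening date and assumed waiting times; it shows sign and rough scale only. A reader might infer that the primary result is affected too. This point gives no ground for that: it concerns what a secondary measure captures, and leaves the One-Back analysis and the 330 patients as they are.

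**What to change.** In 3.4 and 3.6.2:

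1. Name the LLFDI-FC as the physical function outcome and as the baseline mobility modifier. It is already the time-dependent score.
2. Analyse the life-space questions separately, in one of two ways. Either report them descriptively by calendar month and by time from surgery, without attributing change to surgery, or add a calendar-period or dated restriction-stage term to their model. Within a patient, calendar date is surgery date plus time from surgery, so a straight-line calendar term would duplicate the time slope. The term should therefore be in periods or stages.
3. Add the same calendar-period term as a sensitivity analysis in the LLFDI-FC, GDS and NPRS models.

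Cost: wording and some extra modelling. A calendar-period term uses call and surgery dates the study will hold anyway; a restriction-stage term needs outside dates for each site's region. Life space becomes descriptive only, or its surgery estimate becomes less precise. No new patient data are needed.

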APPENDIX I summarizes the study timeline and measurements.

3.4.1 Cogstate Brief Battery (CBB)

The Cogstate Brief Battery (<https://www.cogstate.com>) is a computer-based cognitive test extensively validated against standard neuropsychological batteries in cognitively normal older adults, as well as in patients with cognitive impairment, in the community and in different clinical contexts, both in a clinician/researcher-supervised manner, and in an unsupervised fashion (i.e., through an internet-based self-administration, at home). ⁸⁻¹⁰ It has been used also in the perioperative setting, showing equivalent or greater reliability, and greater sensitivity than conventional batteries.^{11 12} Moreover, In addition to proof of feasibility and acceptability even with older patients with some baseline cognitive impairment, its advantages are short duration (about 15 min), small practice effects (even with monthly assessments), and no ceiling effects.^{8 13} It consists of four tasks (*Detection Task*, *Identification Task*, *Learning Task*, and *One-Back Task*) designed to assess psychomotor function, attention, working memory, and visual learning.¹³ Each task utilizes stimuli in the form of playing cards. Stimuli characteristics (e.g.,

color, suit) are manipulated based on the requirements of each task. The primary performance measure for the *Detection* and *Identification* tasks is reaction time in milliseconds (speed), which is usually normalized using a logarithmic base 10 (\log_{10}) transformation. The primary performance measure for the *Learning* and *One-Back* tasks is the proportion of correct answers (accuracy), which is usually normalized using an arcsine square-root transformation.

Based on industry web standards, the Cogstate system will communicate with the McMaster system through an Application Programming Interface (API), to generate user- and visit- specific links. The CBB will be host in a McMaster webpage, in a seamless fashion for the participant, who will be directed into the Cogstate application when they start the assessment, and then back to the hosting website upon completion of the tests. The CBB will present each cognitive test to the subject following a self-paced training test until valid cognitive data is provided, enabling testing without supervision. Subjects will receive a simple message at the end of their testing session indicating next steps. A detailed report with cognitive data will not be provided to subjects. For the purpose of this study, a support person will be allowed to attend the self-administration of the CBB. This will be established at the enrolment for each participant, and the participant will be instructed to self-administer the CBB under the same conditions at every assessment over time.

After 1-5 days from the initial recruitment and training session, each participant will self-administer the cognitive testing once, and then every month (i.e. 30 days, ± 1 week) until their surgery is performed. We expect that each participant will have at least 2 assessments before surgery. Participants will then self-administer the CBB 1 month, 3 months, 6 months, and 12 months after surgery.

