3.2.1 Inclusion criteria

1. age 65 years or greater
2. patient scheduled to perform noncardiac elective surgery expected to require at least an overnight stay in hospital after surgery
3. surgery deferred, with a known or probable surgery date in ≥6 weeks
4. informed consent provided

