3.5 Sample size

The slowdown of the operating rooms due to COVID-19 started in mid-March, and it will last at least until the end of June or July at the participating sites. We expect to recruit 330 participants between May and August 2020. This sample size will be sufficient to test our primary hypothesis that, on average, in our population, the cognitive performance at 6 months after surgery will be worse, in a clinically significant way, compared to what we would expect based on the preoperative trajectory. We will base our primary hypothesis on the performance at the *One-Back Task (OBK)* of the CBB, at 6 months after surgery. The *OBK* assesses working memory, which is a cognitive domain often found altered in the context of postoperative cognitive dysfunction. It uses a well-validated n-back paradigm with stimuli from playing cards. The subject is asked whether the card displayed in the center of the screen is the same as the card presented immediately before. The subject responds by pressing the “yes” or “no” key. The primary outcome variable for this test is accuracy of correct response, normalized using an arcsine square-root transformation. In **APPENDIX II** we provide a table summarizing the clinical relevance of the test and its results, with data on the difference in performance between healthy older adults, and older adults with mild cognitive impairment (MCI) or dementia based on standardized neuropsychological assessment.^{13 19} Based on the literature, a typical score of healthy older adults is 1.35; the average difference, at one time point, in the *OBK* score, between healthy older adults and older adults with mild cognitive impairment (MCI), and older adults with dementia, is, respectively, 0.07 and 0.17.^{13 19} We hypothesize that in our study population we will see a preoperative trajectory, which, if it continued, unchanged, after surgery (H_0), would lead to an average decrease in OBK score of 0.009 over 6 months. This is still consistent with a decline over time compared with what we would expect on average in a healthy older population.^{13 19} Our hypothesis (H_1) is that surgery will change the preoperative trajectory so that at 6 months after surgery we will instead see an average decrease, compared with right before surgery, of 0.035 (which would correspond to the average change in a hypothetical population in which 40% of subjects experience a decline of at least 0.07, 50% no

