3.6.1 Primary analysis

We will report descriptive summary statistics of the performance of the study population at each of the 4 CBB tasks for each of the preoperative and postoperative time points. We will also represent individual and averaged performance trajectories graphically.

To explore whether surgery has a statistically significant impact on cognitive performance and its trajectories, we will model data using interrupted time series analyses. Interrupted time series analysis is a powerful quasi-experimental design to study the longitudinal effects of interventions or exposures, accounting for pre-intervention/pre-exposure trends. We will adopt the approach described in Kontopantelis *et al.*, *BMJ* 2015.^{21 22} According to this approach we will use regression models in which the within patient performance variation over time is partitioned into three main components, to provide independent tests for the slope in scores in the pre-operative period (test 1); the change in level (i.e., absolute change) around surgery, allowing for the trend before surgery (test 2); and the change in slope from before to after surgery (test 3).^{21 22} The preoperative slope quantifies the trend in performance before surgery. The level change is an estimate of the absolute change in cognitive performance that can be attributed to surgery, i.e., between the time points immediately before and immediately after surgery, and accounting for the preoperative trend. The change in slope quantifies the difference between the preoperative and postoperative slope. Based on the hypothesis that the postoperative trajectory will not be homogenous over the 12 months after surgery, we will also adopt a more complex interrupted time series model that will allow for different slopes of change in different time segments, i.e. right before to 1 month after surgery, 1-3 months, 3-6 months, and 6-12 months after surgery.²³ We will conduct the primary analysis first considering only the early-intermediate postoperative performance (up to 6 months after surgery). With the assumption that the

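### No preoperative cognitive test is timed to the operation, so the plan gives up pre-surgery span that re-timing the last monthly test would recover at little cost

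*Combined protocol and SAP*

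**What the plan says.** Section 3.4.1 starts the preoperative series at enrolment. The first test comes "After 1-5 days from the initial recruitment and training session"; after that, "each participant will self-administer the cognitive testing once, and then every month (i.e. 30 days, ± 1 week) until their surgery is performed". Appendix I shows only a visit at least 6 weeks before surgery and a monthly column. Section 3.6.1 requires at least two preoperative tests for the primary analysis and sets no timing rule relative to surgery. The postoperative tests, in contrast, are counted from the operation: "Participants will then self-administer the CBB 1 month, 3 months, 6 months, and 12 months after surgery".

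A date is available to work with. Inclusion criterion 3 reads "surgery deferred, with a known or probable surgery date in ≥6 weeks", and section 3.4 lists the date of surgery among the data collected.

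The hypothesis and the model both refer to the point of surgery. Section 3.5 expects that "we will instead see an average decrease, compared with right before surgery, of 0.035". Section 3.6.1 places the level change "between the time points immediately before and immediately after surgery", adjusted for the preoperative trend. The plan does not say whether the value at surgery is the last observed score or a projected one.

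**The concern.** The primary question compares the 6-month score with the preoperative line carried forward about 182 days. The precision of that projection depends heavily on the time span of the preoperative tests, which for short waits may be only two tests a month apart. A schedule that runs from enrolment and stops at surgery leaves the last part of the wait unused.

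Cognition, depressive symptoms and pain are also unmeasured in that last part. A change there that does not follow the fitted line enters the level change, which section 3.6.1 attributes to surgery. Neither loss can be repaired once the patient has been operated on.

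**Working it through.** **1. The plan's own sample size.** Inputs from section 3.5: SD 0.16, difference 0.035 − 0.009 = 0.026, two-sided alpha 0.05, power 80%, attrition 10%.

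n = [(1.960 + 0.842) × 0.16 / 0.026]² = 297.2, so 298 evaluable, and 298 / 0.9 gives 332 enrolled. With 330 × 0.9 = 297 completers the power is 0.7997. The stated 330 reproduces, and this point does not change it. I use 297 patients below.

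**2. Gap from last test to surgery.** Suppose intervals X are uniform on 30 ± 7 days from the previous test and surgery falls at random within the cycle.

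- Mean gap = E[X²] / (2E[X]) = (30² + 14²/12) / 60 = 916.3 / 60 = 15.3 days.
- Maximum = 30 + 7 = 37 days. If the tolerance applies to fixed 30-day slots it is 30 + 14 = 44 days. A missed test adds about 30 days.

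The documents give no distribution of waiting times. Simulating the schedule (first test on day 1-5) with assumed uniform waits of 6-10, 6-14 and 6-26 weeks gives a mean gap of 15-16 days, 54-57% of patients over 14 days and 29-32% over 21 days. If every wait were exactly 6 weeks, the mean would be 42 − 3 − 30 = 9 days and the maximum 42 − 1 − 23 = 18 days.

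**3. Precision of the 6-month departure.** The model has a random intercept, a time slope, a level change β₂ and a slope change β₃, with time in days from surgery and tests to 6 months. The departure is β₂ + 182β₃. Total SD is 0.16 (section 3.5); within-patient correlation 0.75 is my assumption. Re-timing moves the last planned test to 3-10 days before surgery, with no test added.

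| Assumed wait | SE as planned | SE re-timed | Reduction |
|---|---|---|---|
| 6-10 weeks | 0.0357 | 0.0296 | 1 − 0.0296/0.0357 = 17% |
| 6-14 weeks | 0.0261 | 0.0228 | 1 − 0.0228/0.0261 = 13% |
| 6-26 weeks | 0.0142 | 0.0134 | 1 − 0.0134/0.0142 = 6% |

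Repeat simulations gave reductions of 6-18% over these scenarios. Correlations of 0.6 or 0.9 change the standard errors but leave the percentage reductions essentially the same.

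**4. Drift over the gap at the plan's own slope.** Section 3.5 assumes that the unchanged trajectory "would lead to an average decrease in OBK score of 0.009 over 6 months". Over 15 days this is 0.009 × 15 / 182.5 = 0.0007, or 2.8% of 0.026. Over 37 days it is 0.0018, or 7.0%.

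**The case against.** **The value at surgery is a model quantity.** A reader might infer that the plan contradicts itself by referring to a moment at which nobody is tested. The documents do not support that. Section 3.6.1 defines the level change through a regression that adjusts for the preoperative trend. The first postoperative test is at 1 month, so the value just after surgery is projected too. Section 3.6.2 states the linearity assumption and plans to examine it. This objection stands.

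**The one-week tolerance already helps.** A reader might also infer that the schedule forces gaps of up to five weeks. It does not. A patient tested on day 33 is next due on days 56-70, so with surgery on day 58 a test on day 56 or 57 is within protocol. If staff used the tolerance whenever they could, the simulated mean gap would be 10-11 days, the maximum about 24, and about 10% of patients would exceed 21 days. For waits of 6-26 weeks the standard error would be 0.0135, so formal re-timing (0.0134) adds almost nothing. For 6-10 weeks it would be 0.0315 against 0.0293, so re-timing still gains. But the plan only permits this use of the tolerance and does not ask for it.

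**The average drift is small, and events are recorded.** Both are true. Step 4 covers only a linear drift, however. Emergency visits and medication changes can be recovered at the 1-month call or from records; cognitive, depression and pain scores from the gap cannot.

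**A late test has drawbacks.** It has high leverage on the slope, and preoperative anxiety could shift it. The GDS measures depressive symptoms, so it would not settle the matter. This stands and calls for a sensitivity analysis.

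**The date may be only probable.** This also stands. Where it is confirmed too late, the current schedule applies and nothing is lost.

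**Conclusion.** This is a cheap design improvement worth making. The plan is not wrong on this point. As written, and without deliberate use of the tolerance, the last test precedes surgery by 15-16 days on average. Re-timing alone would cut the standard error of the 6-month departure by about 6-18%, most for short waits.

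The size rests on assumed uniform waits, a random-intercept model without random slopes, and every surgery date being known in time to move the test. The last of these makes the range closer to an upper limit than an expected gain.

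A reader might go further and take the late test itself as the reference value at surgery. That would replace a trend-based estimate with one noisy score and depart from the analysis in section 3.6.1.

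**What to change.** Add to section 3.4.1 and Appendix I: *once the surgery date is known, the last preoperative CBB, with its call, is timed to fall about 3-10 days before surgery, using the ± 1 week tolerance first and otherwise moving the last planned monthly test. If the date is confirmed too late, the monthly schedule applies.*

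Add to section 3.6.1:

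- Time is coded from actual test and surgery dates, all preoperative tests stay in the model, and the value at surgery is the model-projected one.
- The distribution of the gap from last test to surgery is reported.
- A sensitivity analysis omits the late test in patients who have at least two other preoperative tests.

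The cost is a small amendment and some scheduling work, with no added contact. A moved test may fall more than 37 days after the one before it, so the text should allow that. If surgery is then brought forward, a patient whose second test was moved could be left with one and drop out of the primary analysis, so that test should be moved only when the date is firm.
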